Secondary Aim: Examine the influence of menthol flavor on the effects of nicotine (freebase vs salt) stimulation, craving reduction, and alleviation of nicotine withdrawal. Participants will rate nicotine withdrawal and stimulation using the Revised DEQ and cigarette craving using the gLMS.

Exploratory Aim: Examine nicotine delivery following exposure to nicotine salt vs freebase nicotine exposure in combination with flavors (tobacco or menthol) by measuring saliva nicotine levels 5 min prior and 5, 15, 30, 45, and 55 minutes after nicotine and flavor exposure via e-cigarettes

K01 metabolism study

Eighty-Five African Americans (43 F, 42 M) who smoke and have experience with e-cigarettes will participate in a double-blind, randomized, cross-over study across two experimental sessions. Following overnight abstinence from combustible tobacco products (CO≤10 ppm), participants will be randomly assigned to receive an e-cigarette with menthol flavor or control tobacco flavor (both in a concentration of 5% nicotine) on two separate days. Each session will consist of 1 puffing bout (10 puffs, 3 sec each puff, 30 sec puff interval) followed by 2 hours of abstinence, then 60 minutes of ad libitum e-cigarette use. The specific aims are:

Aim 1: Investigate the relationship of menthol flavor (vs tobacco flavor) and nicotine metabolite ratio (NMR) on nicotine pharmacokinetics and subjective effects during directed e-cigarette administration in African Americans who smoke. We hypothesize that during the menthol exposure session participants will have higher plasma nicotine levels compared to the tobacco flavor exposure session. We hypothesize that NMR is negatively associated with nicotine plasma levels during the tobacco flavor exposure sessions. Lastly, we hypothesize that participants will have a larger reduction of cigarette craving in the menthol compared to tobacco session. Primary outcomes: plasma nicotine boost, nicotine area under the curve. Secondary outcome: cigarette craving. Exploratory outcomes: other subjective effects such as liking of e-cig taste. Gender differences will be explored for all outcomes.

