Experimental Design: Aim 1 focuses on the directed e-cigarette administration procedure. Saliva NMR will be assessed at intake appointment and will be a continuous measure in this study^{59,60}. Following overnight abstinence from combustible tobacco products (CO≤10 ppm), African Americans who smoke will participate in a double-blind, counterbalanced and randomized e-cigarette exposure laboratory study where they will receive two e-liquid flavors (menthol, tobacco) with a fixed nicotine salt concentration in e-cigarettes (5%) on two separate days (one flavor condition per session). The directed e-cigarette administration procedure will consist of 1 fixed-puffing bout (puffing bout=10 puffs, 3 sec each puff, 30 sec puff interval) as done previously by my mentor, [name]. Per the procedures conducted by my co-mentor [name] research group^{62,63}, plasma nicotine levels will be assessed at baseline and 5, 15, 30, 45 and 60 minutes after nicotine exposure via e-liquids during the directed e-cigarette administration procedure. Heart rate and blood pressure will be measured at 5, 15 and 30 minutes after the final puff. Participants will rate irritation/harshness, coolness, cigarette craving, e-cigarette craving, liking of e-cig taste, reward/appeal of e-cig, nicotine withdrawal and stimulation at baseline, 5 and 15 min after nicotine concentration exposure. Participants will be told that they can stop anytime if they feel uncomfortable. **Independent variables:** sex (male or female), nicotine metabolite ratio, flavor (menthol, tobacco), **Dependent variables:** primary outcomes- plasma nicotine boost, nicotine area under the curve; secondary outcomes- cigarette craving; exploratory outcomes- reward/appeal of e-cigs, e-cig craving, irritation/harshness, coolness, nicotine withdrawal, stimulation, liking of e-cig taste. We will explore gender differences for all outcomes.

Aim 2: Elucidate the relationship between menthol flavor (vs tobacco flavor) and NMR on nicotine pharmacokinetics and subjective effects during e-cigarette ad libitum use

Eligibility/ Recruitment/Screening: African Americans who participate in Aim 1 will participate in Aim 2.

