Experimental Design Aim 2 focuses on the ad-lib e-cigarette exposure. Saliva NMR will be assessed at intake appointment. For each lab session, 120 min after the directed e-cigarette exposure period (Aim 1) participants will undergo a 60 min ad-lib e-cigarette exposure session. For each lab session, each participant will be exposed to the same JUULpods they were exposed to during the directed e-cigarette exposure period. During the ad-lib e-cigarette period, participants can freely self-administer the e-cigarette. The ad-lib period will be video recorded to record puffing behaviors. E-liquids will be measured before and after the session. Two research assistants will independently code the videotapes for puffing behaviors. Participants will be told that they can stop anytime if they feel uncomfortable. Plasma nicotine levels will be assessed at baseline and 15, 30 and 60 minutes after the start of the ad-lib e-cigarette exposure period. Participants will be told that they can stop anytime if they feel uncomfortable. Smoking cessation materials/programs will be offered at the end of the study. **Independent variables:** sex (male or female), nicotine metabolite ratio, flavor (menthol, tobacco), **Dependent variables:** primary outcomes- plasma nicotine boost and nicotine area

under the curve. Secondary outcomes- measure of nicotine delivered to participant and cigarette craving. exploratory outcomes- number of puffs and subjective effects as mentioned in Aim 1. We will explore gender differences for all outcomes

The JUUL™ and menthol and tobacco JUUL pods™[5%(59mg/ml)] will be used for this study. The JUUL™ is one of the most widely used pod e-cigarette devices^{57,58}. Participants will not be allowed to keep the device.

Figure 1: Study Experimental Design

[figure not shown]

Figure 1 Legend: Depicts the time for each lab session. Participants will undergo two lab sessions. Participants will receive two e-liquid flavors (menthol, tobacco) with a fixed nicotine salt concentration in e-cigs (5%) on two separate days (one flavor condition per session).

Assessments

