subjects in total (43 women, 42 men) we will have 80% power at two-sided alpha level 0.05 to detect a correlation of 0.30 or bigger in absolute value between NMR and the primary study outcomes. For the within subject comparisons of the tobacco and menthol flavor sessions, with 85 individuals we will have 80% power at two-sided alpha level 0.05 to detect a medium effect size (Cohen's $d=0.32$) for the primary study outcomes. This is a cross-over study, so all 85 participants will participate in Aim 1 and Aim 2 of this K01 proposal.

SECTION II: RESEARCH INVOLVING DRUGS, BIOLOGICS, RADIOTRACERS, PLACEBOS AND DEVICES

If this section (or one of its parts, A or B) is not applicable, check off N/A and delete the rest of the section.

A. RADIOTRACERS N/A

1. Name of the radiotracer: *Write here*
2. Is the radiotracer FDA approved? YES NO

If NO, an FDA issued IND is required for the investigational use unless RDRC assumes oversight.

B. DRUGS/BIOLOGICS N/A (IND not applicable; ITP assessed)

TCORS Menthol Pilot Study

The Suorin iShare™ and available e-liquids will be used for this study. The Suorin iShare™ is a refillable pod system e-cigarette device composed of a battery without voltage control and a refillable pod that contains the e-liquid, mouthpiece and coil. It is among one of the pod e-cigarette devices that are used widely^{57,58}. We have received an ITP from the FDA to use this e-cigarette device.

The following e-liquids will be purchased from e-liquid from American eLiquid Store:

- 1) DuraSmoke® Tobacco Menthol eLiquid 36mg/ml
- 2) Tobacco - Menthol eLiquid AmericaneLiquid® 36mg/ml
- 3) DuraSmoke® Tobacco Virginia eLiquid 36mg/ml
- 4) Tobacco - Virginia Flue Cured eLiquid AmericaneLiquid® 36mg/ml

We have received documentation from the American eLiquid Store stating that the above e-liquids were on the market prior to August 2016 so we do not need an ITP for these e-liquids.

K01 Metabolism Study

The JUUL™ and JUULpods™[5%(59mg/ml)] will be used for this study. The JUUL™ is one of the most widely used pod e-cigarette devices^{57,58}. We do not need an ITP from the FDA to use this e-cigarette device and products as they predate the enforcement compliance date.

The following JUULpods will be purchased:

- 1) Menthol eLiquid 59mg/ml (5%)nicotine

2)VirginiaTobacco eLiquid 59mg/ml (5%)nicotine

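### K01 study: two primary outcomes per aim with no success rule, so the two-sided false-positive rate is about 7-9% per Aim 1 hypothesis, not 5%

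*Combined protocol and SAP*

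**What the plan says.** Section I.1 lists for K01 Aim 1: "Primary outcomes: plasma nicotine boost, nicotine area under the curve". The same pair is listed there for Aim 2. Section I.4 repeats the pair under the Aim 1 design ("primary outcomes- plasma nicotine boost, nicotine area under the curve; secondary outcomes- cigarette craving") and under the Aim 2 design ("primary outcomes- plasma nicotine boost and nicotine area", the second measure being the AUC). The item on plasma nicotine in the Section I.4 assessment list derives both measures from one set of blood samples.

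Aim 1 has two directional hypotheses about plasma nicotine. For flavor: "during the menthol exposure session participants will have higher plasma nicotine levels compared to the tobacco flavor exposure session". For NMR: "We hypothesize that NMR is negatively associated with nicotine plasma levels during the tobacco flavor exposure sessions". Both refer to plasma nicotine levels in general, and neither selects boost or AUC.

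The power paragraph in Section I.13 gives, for N=85, "we will have 80% power at two-sided alpha level 0.05 to detect a correlation of 0.30 or bigger in absolute value". That statement concerns NMR and refers to the primary outcomes in the plural. For the flavor comparison it says that "with 85 individuals we will have 80% power at two-sided alpha level 0.05 to detect a medium effect size", given as d=0.32, again for the primary outcomes in the plural. The K01 analysis text in the same section specifies mixed models with NMR, time, flavor and their interactions. It contains no ordering of the two outcomes, no requirement that both succeed, no adjustment and no other definition of success.

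**The concern.** Two outcomes serve one hypothesis, the only significance level in the plan is 0.05, and no rule links the outcomes to the conclusion. A report could follow this plan to the letter and claim support for a hypothesis from whichever of boost and AUC reaches p<0.05, with the choice made after the data are seen. The error rate behind that claim is then higher than the 5% on which the power figures rest. K01 states directional hypotheses, is powered on these outcomes and is meant to inform regulation, so the rate attached to its primary claims matters.

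**Working it through.** **Inputs.** N=85, two-sided alpha 0.05, 80% power, r=0.30 and d=0.32 (Section I.13). Two primary outcomes per aim and two Aim 1 hypotheses on plasma nicotine (Section I.1). The boost-AUC correlation is not given in the documents. I assume a range of 0.5 to 0.9 and show independence as the limiting case.

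**The plan's own figures.**
- NMR, Fisher z: power = Φ(atanh(0.30)·√(85−3) − 1.960) = Φ(2.803 − 1.960) = 80.0%. The stated figure reproduces.
- Flavor, paired t with 84 df and noncentrality 0.32·√85 = 2.950: power 83.1%. The stated 80% is slightly conservative; d of about 0.31 would be detectable at 80%.

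Each calculation is for one test at 0.05, so neither allows for a second outcome.

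**False-positive rate for one hypothesis when either outcome suffices.** With both nulls true, p = 1 − Pr(|Z₁| ≤ 1.96 and |Z₂| ≤ 1.96), where Z₁ and Z₂ are bivariate normal with correlation ρ.

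| ρ (assumed) | two-sided rate | in the hypothesized direction (half) |
|---|---|---|
| 0 | 1 − 0.95² = 9.8% | 4.9% |
| 0.5 | 9.1% | 4.5% |
| 0.7 | 8.3% | 4.2% |
| 0.9 | 7.0% | 3.5% |

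**Effect of Holm within a hypothesis.** The smaller of the two p-values is tested at 0.025. At that level with N=85:
- NMR: Φ(2.803 − 2.241) = 71% power at r=0.30, against 80% at 0.05. The detectable effect at 80% power is tanh((2.241 + 0.842)/√82) = 0.33.
- Flavor: 75% power at d=0.32, against 83% at 0.05. The detectable effect at 80% power is d=0.34.

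These are figures for a single test at 0.025. They understate the power of the full Holm procedure, which tests the second outcome at 0.05 once the first is rejected.

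**What remains across both Aim 1 hypotheses after the fix.** The flavor and NMR tests are treated as independent under the null.
- Holm within each hypothesis: the rate per hypothesis is 4.65% at ρ=0.5 and 3.62% at ρ=0.9. Over the two, 1 − (1 − 0.0465)² = 9.1% and 1 − (1 − 0.0362)² = 7.1%.
- Single primary for each hypothesis: 1 − 0.95² = 9.8%.

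**The case against.** **Direction.** The Aim 1 hypotheses are directional, so a significant result in the wrong direction confirms nothing. Counting only the hypothesized direction, the chance of a false confirmation is 4.5% to 3.5% per hypothesis over the assumed range, below 5%. The arithmetic is right and belongs beside the 7-9%. It does not remove the gap, because the plan sets its level as two-sided 0.05, and on that definition the rate is exceeded.

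**Pooling.** A reader might infer that Aim 1 carries a false-positive risk of 14-17%, by counting four tests (two outcomes for each of flavor and NMR): 1 − (1 − 0.091)² = 17% and 1 − (1 − 0.070)² = 14%. The documents do not support that as the headline. They state flavor and NMR as separate hypotheses with separate power statements, and nowhere present them as one family. The pooled figure also needs all four nulls to be true and counts rejections in either direction.

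**Inferred tests.** Alpha 0.05 appears only in the power paragraph. The analysis text describes mixed models, not stand-alone correlation and paired tests. That is so, and the calculation above is a simplification of those models. But 0.05 is the only level the plan gives, and the analysis text supplies no other rule.

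**Both may be required.** If both outcomes must be significant, the inflation disappears. The plan does not say so, and the 80% figures would then hold for each outcome, not for joint success.

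**Nature of the study.** This is a mechanistic laboratory study, and boost and AUC summarize one construct. That argues for modest severity. It also makes it easy to choose one of them, although the documents give no ground for preferring either.

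**Conclusion.** The point holds for each hypothesis taken separately. As written, and if either outcome can support the claim, each Aim 1 hypothesis (flavor, or NMR) carries a two-sided false-positive rate of about 7-9% where the plan states 5%. This rests on an assumed boost-AUC correlation of 0.9 to 0.5; independence gives about 10%. Half of the rate is in the direction opposite to the hypothesis.

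The figure is calculated for Aim 1. Aim 2 names the same two outcomes and has the same missing rule, but its plasma hypothesis is that levels are similar between flavors, so the rate does not carry over directly. This is an inexpensive improvement that should be made, not a defect that invalidates the design.

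**What to change.** Before analysis, add to the K01 part of Section I.13 one of the following:

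1. **Single primary.** For each hypothesis, name either boost or AUC as the one primary outcome and make the other secondary. The stated power figures then stand.
2. **Holm.** Apply Holm across boost and AUC within each hypothesis. State that at the first-step level of 0.025 with N=85, a single test has 80% power for r=0.33 and d=0.34, with 71% at r=0.30 and 75% at d=0.32 (against 80% and 83% at 0.05). Label these as conservative, because the second outcome is tested at 0.05 after the first rejection.

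Under either option, state that flavor and NMR are treated as separate questions. Error is then held at 5% for each hypothesis but not across Aim 1 as a whole, where about 7-9% remains under Holm and about 10% with a single primary. State the rule for Aim 2 as well.

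The cost is a few sentences, with no added participants, visits or samples. The downside of Holm is slightly less favorable detectable effects. With a single primary, the other outcome can no longer carry the primary claim.

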Experimental design: This proposal seeks to elucidate the differences in reward/appeal, harshness/irritation, nicotine delivery, preference and impact of menthol flavor (compared to control tobacco flavor) between nicotine salt vs free base nicotine e-liquids. Thirty adult menthol smokers (15 male; 15 female) will participate in a double-blind, randomized, cross-over study across three experimental sessions. For the first two sessions, each participant will be randomly assigned to receive nicotine salt or freebase nicotine (both in a concentration of 36mg/ml) on two separate days (see Table 1). Freebase nicotine e-liquid at concentration of 36mg/ml has been used previously in

smokers with no reported adverse effects^{53,54} and this concentration is within range of nicotine concentrations used in nicotine salt e-liquids/e-cigarette pod devices^{55,56}. Following overnight abstinence from combustible tobacco products (CO≤10 ppm), participants will be exposed to the assigned form of nicotine in combination with two flavor conditions (tobacco and menthol) in a counterbalanced randomized order. Each exposure will consist of 2 2-sec puffs and will be separated by a 60-minute washout period (see Table 2).

iSaliva nicotine/ cotinine is an exploratory outcome and nicotine/cotinine levels will be assessed using saliva samples obtained 10 times per session (5 min prior to and 5, 15, 30, 45, and 55 minutes after the onset of puff1, and 5, 15, 30, and 45 minutes after the onset of puff2). Assessing the nicotine/cotinine levels will determine if there are pharmacokinetic differences between nicotine salts vs freebase nicotine. After completing the first two e-cigarette exposure sessions, the same thirty adult menthol smokers (15 female, 15 male) will undergo overnight abstinence from combustible tobacco and nicotine products and participant in a 60-minute choice e-cigarette self-administration session.

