After the e-liquids are received, they will be delivered and stored in appropriate light/temperature conditions at John Pierce Labs, which is a secured building. The liquids will be kept in a locked storage container in a drawer within the lab room. On the day prior to the lab sessions, a research assistant/associate/fellow who is not involved in the actual conduct of the lab sessions will fill the e-cigs. The information on randomizations to nicotine condition and flavors for each experimental session has been generated by study biostatisticians. This information is stored for each participant in an individual envelope and a printed study ID on the cover. These envelopes are stored at Pierce lab along with the purchased e-liquids. The individual filling the pods will be notified of which subject ID number needs to be filled and they will then go to Pierce labs and open the envelope and fill the three pods with the appropriate e-liquids. First, they will label each pod with the study ID number and lab 1 and 2 respectively. Each bottle of e-juice will be shaken vigorously prior to filling the pods. Next, they will open the top of the pod and using a mechanical pipette will load .9ml into the pipette from the e-juice bottle and carefully transfer it into the pod. This will be completed for all lab sessions. Each pod is then stored in a separate airtight bag to avoid cross contamination of flavors. The individual bags are then stored together in a larger bag labeled with the study ID number and stored back in the locked container until the lab is set to begin. Once the research assistant is ready to begin each lab, they will open the locked container, take the appropriate pod and leave the others. At the end of the lab, they will return the pod used that day to its proper bag and again return it to the lock box. None of the e-juice or pods will be transported outside of Pierce lab. The research staff will have the group randomization list and will dispense the appropriate e-liquid (nicotine condition, flavor) needed for each subject.

K01 Metabolism Study

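### The TCORS pod procedure fills three pods where sessions 1 and 2 alone need four, gives no first/second label, and leaves unclear whether session staff hold the randomization list

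*Combined protocol and SAP*

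**What the plan says.** All references are to the combined protocol and SAP, TCORS menthol pilot study.

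**Design (Section I, item 4, Research Plan, with Tables 1 to 3).** Each of the first two sessions uses one nicotine form, salt or freebase. Within the session, "participants will be exposed to the assigned form of nicotine in combination with two flavor conditions (tobacco and menthol) in a counterbalanced randomized order". In session 3 the participant may use any of the four liquids, from e-cigarettes lettered A to D by an assistant who neither runs the study nor codes the videos. The study is called double-blind; the detail that follows names only the subjects.

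**Preparation (Section II.B, item 4, Storage, Preparation and Use).** The day before the sessions, someone with no part in running them is to "open the envelope and fill the three pods with the appropriate e-liquids". On labels: "First, they will label each pod with the study ID number and lab 1 and 2 respectively". On scope: "This will be completed for all lab sessions". At the session, the research assistant is to "take the appropriate pod and leave the others", and afterwards "they will return the pod used that day to its proper bag". The paragraph ends: "The research staff will have the group randomization list and will dispense the appropriate e-liquid (nicotine condition, flavor) needed for each subject".

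**Pod supply (Section II.B, item 2, Background Information).** Each experiment is to have new pods. The term *experiment* is not defined.

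**The concern.** The preparation text does not fit the design it serves, in three respects.

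1. **Count.** Three pods cannot hold four different liquids, and no refilling is described.
2. **Order.** Two pods for the same lab would carry the same study ID and lab number. Nothing stated marks one as first and the other as second.
3. **Access to the list.** The order could be recovered from the randomization list, which names form and flavor. If the person running the session holds it, that person is not blind, and having an uninvolved filler serves little purpose.

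The primary aim concerns self-rated irritation/harshness, liking and wanting of drug effects, and liking of the flavor, compared by flavor and nicotine form. Flavor is compared within a session. A pod that is missing, or used in the wrong position without being noticed, would therefore leave a condition undelivered, attach ratings to the wrong flavor or disturb the counterbalancing. Staff who know the liquid could also influence subjective ratings.

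**Working it through.** No power, alpha or sample-size figure is involved. The check is a count, followed by a comparison of passages.

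**Inputs**
- Nicotine forms: 2, one per session in sessions 1 and 2 (Research Plan).
- Flavors per session in sessions 1 and 2: 2, in randomized order (Research Plan; the heading of Table 2 also gives two conditions per session).
- Liquids offered in session 3: 4 (Research Plan, Table 1).
- Pods filled: 3; label: study ID and lab number; pods taken and returned per lab: described in the singular (Storage, Preparation and Use).

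**Reproducing the plan's figure.** One pod per session over three sessions gives 1 x 3 = 3, which also agrees with the singular wording on taking and returning a pod. It was the only reading found that gives 3. It allows 1 liquid per lab in sessions 1 and 2 where 2 are needed, and 1 in session 3 where 4 are needed. The stated labels, moreover, name only labs 1 and 2.

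**What the design needs**
- Distinct liquids: 2 forms x 2 flavors = 4.
- Pods for sessions 1 and 2: 2 sessions x 2 flavors = 4, one more than stated.
- All three sessions, pods reused in session 3: 4.
- All three sessions, new pods in session 3: 4 + 4 = 8, five more than stated.

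**What three pods could deliver.** There are four ways to choose three of the four liquids. Each leaves one nicotine form with both flavors and the other with only one. So exactly 1 of the first two sessions would be complete.

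**What the labels carry.** Nicotine form is constant within a session, so the lab number is enough to separate the forms. It does not separate the two flavors within a lab. That leaves 2 possible orders per lab and 2 x 2 = 4 across labs 1 and 2.

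**Who can resolve the order.** The filler opens the envelope with the allocation, but no position mark is described that would pass the order on. The session assistant has to pick the right pod. The only stated source that identifies it is the list given to the research staff.

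**The case against.** The strongest reply is that this is a storage paragraph in an ethics-board template. The design itself is coherent, and the study is a pilot with a target of 30 completers, meant to estimate effects for a larger study. Several parts of that reply stand.

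- **Pod reuse is possible.** A reader might infer that 8 pods are required. That holds only if *experiment* means session. Used pods go back to their bags and the lock box, and each exposure in sessions 1 and 2 is two 2-second puffs from a 0.9 ml fill. Reuse is not stated, but it is not excluded. The firm minimum is 4.
- **Nobody is said to guess.** A reader might infer that half the sessions would run in the wrong order. That assumes a blind pick between identically labelled pods. No passage describes one, and the text supplies a list, so no error rate can be attached.
- **Labels may be fuller in practice.** Each pod has a separate bag and returns to its proper one, which suggests that bags can be told apart. No bag code is written down. The finding is that the stated labels lack a position, not that no code exists.
- **Unblinded session staff are not established.** A reader might infer that they are. The text says research staff, and the filler may also be a research assistant. Against reading the sentence as meaning the filler, nearly the same sentence appears for the K01 study, where a pharmacist dispenses and is distinct from the research staff. The TCORS session assistant must also choose the pod. Session staff are the natural reading, but not the only one.
- **Some safeguards exist.** The magnitude and hedonic ratings are entered on a computer screen, staff speak to participants from another location, and session 3 is already coded A to D. These limit staff influence on ratings. They do nothing for the pod count or for the order in labs 1 and 2.

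It might also be inferred that consulting the list would put everything right. It would settle the order, but it cannot make three pods hold four liquids.

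**Conclusion.** The preparation text contradicts the Research Plan and cannot be followed as written. It provides 3 pods; sessions 1 and 2 alone need 4, and all three sessions need 4 or 8 depending on reuse. This conclusion takes the Research Plan's two flavors per session and four liquids in session 3 as intended, and assumes no refilling, since none is described.

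The stated labels give no first or second position for labs 1 and 2. The only stated remedy is a list of form and flavor held by the research staff. If that includes session staff, it conflicts with the double-blind description and with the use of an uninvolved filler. This is a risk that the text leaves open, not a demonstrated loss of the blind, and the documents give no basis for quantifying bias.

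The point merits correction because the primary outcomes are subjective and the repair costs almost nothing. It does not alter the sample size or the planned models.

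**What to change.** Amend the TCORS text under Storage, Preparation and Use, and reconcile it with the Research Plan and with the statement on new pods under Background Information:

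1. Correct the number of pods to match the design, and state whether the pods from sessions 1 and 2 are reused in session 3 (4 in total) or replaced (8 in total).
2. Have the uninvolved filler label the lab 1 and 2 pods by study ID, session and position (1-first, 1-second, 2-first, 2-second), with nothing that reveals form or flavor.
3. Describe taking and returning two pods, not one, at each of labs 1 and 2.
4. Keep the existing A-D coding for session 3.
5. Restrict the randomization list to the filler and the biostatisticians, and say that session staff do not hold it.

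The cost is revised wording and labels. No new staff are needed, because the uninvolved filler is already in the plan.
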